1.6 Study Rationale and Appropriateness of Measurements

Results from Phase 2 studies and the associated OLE study have shown that SPN-810 added to optimized ADHD therapy resulted in remission of aggression and significantly improved impulsive aggressive behavior in children with ADHD, in addition to exhibiting a good tolerability profile in children with ADHD and associated feature of IA.

This Phase 2 (810P204) study seeks to evaluate the effect of 4-week SPN-810 treatment on brain functioning in patients aged 8-12 years with ADHD and associated feature of IA. This will be achieved using fMRI in conjunction with the PSAP Task, a behavioral aggression paradigm in which subjects are provoked by having money indirectly taken from them by a (unbeknownst to the subject) fictitious opponent during a money acquisition task.

The PSAP Task is a well-established test for evaluating aggressive behavioral responses related to IA, and has been previously used in fMRI studies to elucidate the neural activation involved in aggressive behaviors (Bubenzer-Busch et al., 2015; Cherek et al., 1997; Skibsted et al., 2017; Cunha-Bang et al., 2017; Kose et al., 2015).

The PSAP Task parameters for this study (810P204) were optimized in a non-interventional Study (810P204a) conducted in typically developed children 8-12 years old.

Prospective evaluation of subjects using well-established diagnostic tests will confirm that enrollees have both ADHD (by MINI-KID) and moderate to severe IA (by R-MOAS, CGI-S, and the Vitiello Aggression Scale). Subjects in this double-blind, placebo-controlled, 2-arm, randomized (1:1), parallel-group will receive study medication twice daily (BID) with or without food. Enrolled subjects will follow a titration schedule that has been shown to be safe, efficacious, and well-tolerated in a similar patient population in a previous Phase 2b study.

Safety will be assessed by the monitoring of AEs, vital signs, ECGs and clinical laboratory tests, as well as by the Simpson-Angus Scale, the Barnes Akathisia Rating Scale (BARS), the Abnormal Involuntary Movement Scale (AIMS), and the Columbia-Suicide Severity Rating Scale (C-SSRS).

The effect of Molindone on body composition, metabolic parameters, and prolactin will be evaluated.

2 STUDY OBJECTIVE

2.1 Primary Objective

The primary objective of Study 810P204 is to evaluate the effect of SPN-810 treatment on brain activity in subjects aged 8-12 years with ADHD and IA using fMRI.

2.2 Secondary Objectives

The secondary objectives are to evaluate the effect of SPN-810 treatment on:

- The functional connectivity between brain regions using resting-state fMRI (rs-fMRI)
- The concentration of neurotransmitters glutamate and GABA using MRS
- The safety of SPN-810

2.3 Tertiary Objectives:

Tertiary objectives are to evaluate the following:

- •
- Effect of SPN-810 treatment on CGI-S and CGI-I scores
- Effect of SPN-810 treatment on the R-MOAS score

3 INVESTIGATIONAL PLAN

3.1 Overall Study Design

This is a multi-center, randomized, double-blind, placebo-controlled, 2-arm, parallel-group study to evaluate the functional effect of SPN-810 treatment on IA in subjects aged 8-12 years diagnosed with ADHD in conjunction with approved ADHD medication. Figure 1 and Figure 2 depict the study design schematically.

This study consists of 3 phases: Pre-Treatment, Treatment, and Conversion/Taper.

The Pre-Treatment Phase comprises of Screening and a Baseline MRI Visit for a total duration of up to 30 days. Following Screening (Visit 1), eligible subjects will proceed to the Baseline MRI visit (Visit 2) at the Imaging Center, where the brain MRI scans will be performed. At Visit 3, eligible subjects will be randomized to study medication or placebo.

Eligible subjects will follow a dose-titration schedule as shown in Figure 1 and Figure 2, with dosing starting at and increasing approximately every 2 days until the target dose (36 mg/day) is reached. The final dose will be maintained for 2 weeks (Maintenance period) during which time subjects will return for PK sampling (Visit 4) prior to receiving the final MRI scan at the Imaging Center (Visit 5). At the intervening visit during the maintenance phase (Visit 4), subjects will be given the option to taper down/discontinue study medication or convert to an ongoing OLE study (810P304) upon completion of the current study and will receive the blinded taper or the conversion study medication kit.

Subjects will return to the study site for a final EOS visit (Visit 6), after completing the 1-week Taper or Conversion phases. Subjects who choose to convert into the ongoing OLE (SPN-810 304) will enter the study at a dose of 18 mg/day SPN-810.

A subject who discontinues early in the Maintenance period, i.e., prior to Visit 5, may be allowed to participate in the OLE on a case-by-case basis after consultation by the Investigator, Medical Monitor, and Sponsor.

Safety will be assessed by the monitoring of AEs, vital signs, ECGs and clinical laboratory tests, as well as by the Simpson-Angus Scale, the Barnes Akathisia Rating Scale (BARS), the Abnormal Involuntary Movement Scale (AIMS), and the Columbia-Suicide Severity Rating Scale (C-SSRS). These scales were chosen to specifically monitor EPS, since youths treated with antipsychotics are at greater risk for EPS side effects than adults (Findling et al., 2005). The Simpson-Angus Scale, BARS, and AIMS were utilized in Phase 2 studies and have been used in other clinical studies of atypical antipsychotics in children (Sikich et al., 2008; Stocks et al., 2012).

3.2 Imaging Acquisition and fMRI Set-up

This study is designed to use fMRI in conjunction with the PSAP aggression task. MR imaging parameters for the PSAP Task were optimized in the non-interventional 810P204a study that was conducted by the Sponsor in typically developing children 8-12 years of age.

3.2.1 BOLD fMRI

BOLD fMRI is a method used to investigate brain activity by measuring the change in blood oxygenation. When a brain area is active, the flow of oxygenated blood increases to that region in response to increased oxygen demand. Changes in the relative levels of oxyhemoglobin and deoxyhemoglobin can be detected due to their differences in magnetic susceptibility. Deoxygenated hemoglobin is paramagnetic while oxygenated hemoglobin is diamagnetic. An Echo-Planar Imaging (EPI) MRI sequence is sensitive to changes in magnetization (T2*) and can therefore be used to measure blood oxygenation as a proxy for brain activity.

This technique can be used during task-based fMRI, where the T2* contrast between a task and control condition can be used to identify regions of the brain that show a change in oxygenation as a result of the task. BOLD fMRI is therefore highly spatially selective, but less temporally specific (due to the slow time-course of blood flow). For instance, it can be used to see what regions are active during viewing of aggressive scenes, or what regions of the brain become active during a choice-inhibition task. Subsequently, the difference in the strength, location, or extent of brain activation between groups can be assessed.

Another approach to assessing brain function is resting-state BOLD fMRI (rs-fMRI), where BOLD fMRI is measured during rest (during which the participant looks at an image of a crosshair during an 8-minute scan). Rs-fMRI can be used to study brain networks by looking at correlations in the time-course of the spontaneous BOLD signal time-courses 'at rest' between

different regions of the brain. These networks are thought to have specific functions and are considered connected, and many have been identified (e.g., the default mode network, executive control network, praxis network). Studies of different disorders have shown differences in the functional connectivity in these networks in different populations and can be indicative of differences in brain function.

3.2.2 Point Subtraction Aggression Paradigm (PSAP) Task

The PSAP is a behavioral aggression paradigm in which each subject competes against a fictitious opponent (in reality, the computer) to earn points. At the start of the task, subjects will be instructed that they and another subject of the same age, who is located in a different building, will be competing to earn as many as points as possible. Subjects are told that they will win prizes for their participation and can win additional prizes (money) if they complete the task. The subjects can press 1 of 3 buttons on a keypad (Option 1, 2 or 3) a set number of times to achieve a specific outcome.

The PSAP Task will be presented using custom E-Prime 3.0 software (Psychology, Software Tools Pittsburgh, PA) developed by [name] Lab at Northwestern University in Chicago. The program will be run from a laptop computer synchronized to the MRI scanner.

During each study visit at the Imaging Center, subjects will complete two PSAP-fMRI sessions, each lasting 12 minutes. For each run, the subject can remove points from his or her opponent (simulating aggressive behaviors) or have points stolen by the opponent (i.e., provocations). Options 1, 2 and 3 correspond to the index, middle, and ring finger of the dominant hand. The game status is presented on a screen, which includes the numbers of points earned and the current number of button presses.

By pressing the button for Option 1, 100 times, the subject will earn a point (\$1.00); pressing the button for Option 2, 20 consecutive times is the aggression action that results in stealing a point (\$1.00) from the opponent; pressing Option 3, 20 times protects the subject from the opponent's attempt to steal points (i.e., money) for a 60 second time frame. Once an option is selected, subjects are required to complete that option before choosing a new option. There will be a minimum of 170 ms between button presses to regulate how quickly they can choose the button to press. Provocations can occur at any time during the game and will be spaced at least 6-60s apart depending on the participant's use of the protection option.

When subjects reach 100 consecutive button presses, black flashing points ('+') are presented around the point total, which will then increase. When the subjects are provoked by having a point stolen, a red flashing '-' sign is displayed around the point total.

3.2.3 Data Acquisition

All scanning will be performed on a Siemens-Skyra 3T MRI scanner using a 32-channel head coil. Functional images for the PSAP Task will be collected at an angle of 30° from the anterior commissure-posterior commissure (AC-PC) axis, which reduces signal dropout in the

orbitofrontal cortex (Deichmann et al., 2003). Seventy-two slices will be acquired at a resolution of 2 mm x 2 mm x 2 mm, providing whole-brain coverage. A GRE EPI pulse sequence will be used (repetition time (TR) = 2000 ms, echo time (TE) = 25 ms, multiband factor of 2, field-of-view = 220 mm, flip angle = 80°).

Resting-state data will be collected using a similar sequence for a duration of 8 minutes.

Physiological measures of respiration and/or blood oxygen saturation will be measured during the scans to clean rs-fMRI data from physiological noise arising from these sources (Murphy et al., 2013).

3.2.4 Magnetic Resonance Spectroscopy (MRS)

MRS relies on the observation of hydrogen protons, which have a magnetic moment when placed in a magnetic field (such as the MRI scanner). Water is the most abundant hydrogen-containing compound in the brain, but when the water signal is suppressed, other H-proton-containing metabolites can be observed. MRS allows for the measurement and therefore quantification of different metabolites within the human brain. An MRS spectrum contains all metabolites from a predefined region of brain tissue plotted along a chemical shift axis.

3.2.4.1 GABA and Glutamate Brain Concentrations

GABA and Glu are the human brain's primary inhibitory and excitatory neurotransmitters, respectively, and play a key role in driving and regulating brain activity and function. While detectable using MRS, GABA and glutamate, though found at abundant concentrations in the human brain, have signals that overlap and are obscured by larger signals in conventional spectra. Therefore, use of conventional PRESS (Bottomley et al., 1987) sequence acquisition will be enhanced by dual echo time scheme, which allows additional information to be obtained on the spectral characteristics of the metabolites, lipids, and macromolecules. Furthermore, advanced numerical simulations that predict the exact pattern of the metabolites would be used during data fitting, which facilitates deconvolution of the spectral content (Kaiser et al., 2008; Veshtort et al., 2006). In this study, glutamate (Glu) concentrations will be measured using advanced fitting software on the spectra.

Due to the low sensitivity of MRS, these measurements are typically made from a large voxel in an approximately 8-minute scan duration to obtain sufficient signal to noise ratio to reliably estimate these neurotransmitters. There is no additional risk involved as this is a typical MRI scan protocol. Data will be acquired from the anterior cingulate cortex (ACC) region.

3.2.4.2 MRS Data Acquisition

MRS data will be acquired on a Siemens-Skyra 3T MRI scanner. Prior to MRS, a T1 Magnetization-Prepared Rapid Acquisition with Gradient Echo (MPRAGE) will be acquired for voxel localization. MRS will be acquired in the ACC (Ende et al., 2016).

A spatial localization in PRESS is performed using a 90° Hamming-filtered sync pulse (bandwidth time product = 8.75, duration = 2.12 msec, bandwidth [FWHM] = 4.2 kHz) and two 180° mao

pulses (duration = 5.25 msec, bandwidth = 1.2 kHz). All localization pulses are executed at 3 ppm. The sequence will utilize two echo times (TE=23 ms and TE=140 ms, with TR=4 s).

Variable power with optimized relaxation delays (VAPOR) and outer volume suppression are used to suppress water and to improve the localization of the volume of interest. The model spectra will be created using state-of-the art software Spinevolution, which employs advanced numerical simulation algorithms. Experimental parameters, such as echo time, pulse sequence delays, and RF pulse shapes will be utilized within the simulation to reproduce experimental conditions as close as possible (https://spinevolution.com). Other software packages may be used as needed to analyze the MRS data.

The analysis allows the calculation of the best fit of the experimental spectrum as a linear combination of model spectra. All metabolites (including GABA and Glu) will be calculated from the combined spectral information from dual echo time scheme.

The concentrations of the different metabolites of interest are expressed as ratios over creatine (Cr).

3.3 Duration of Study Treatment

The total subject duration on study: approximately 9 weeks.

Pre-treatment Phase: Up to 30 days

Screening: 1 day
 Baseline MRI: 1 day
 Treatment Phase: 28 days

Titration Period: 14 days Maintenance Period: 14 days

Taper/Conversion Phase: 7 days

Figure 1: Study Schematic: Conversion to Open-Label Extension Study

[figure not shown]
[figure not shown]

Figure 2: Study Schematic: Taper and Complete/Discontinue

This document is confidential. It contains proprietary information of Supernus® Pharmaceuticals, Inc. Any viewing or disclosure of such information that is not authorized in writing by the Sponsor is strictly prohibited. Such information may be used solely for the purpose of reviewing or performing this study.

3.4 Pre-Treatment Phase (Up to 30 days)

3.4.1 Screening Period (Up to 30 days): Visit 1, Day -30

Screening procedures will be conducted approximately 30 days before titration, and may be carried out over more than 1 visit if needed. Prior to conducting any study-related procedures, a written Informed Consent/Assent must be obtained from the subject's parent or legal representative, and the subject (when required). Abnormal results on screening laboratory tests may be repeated at the discretion of the Investigator and the Medical Monitor. Each screened subject will be assigned a subject number in a sequential order.

The population will be male and female subjects with IA and diagnosed with ADHD, currently being treated with an FDA-approved standard ADHD treatment. In addition, subjects who had qualified to participate in 1 of the ongoing double-blind Phase 3 studies (CHIME 1 and CHIME 2) but screen failed (i.e., non-compliance with the electronic diary or currently on ADHD treatment with more than one FDA-approved medication) may be eligible to participate in the 810P204 study if they meet the study criteria.

The diagnosis of ADHD will follow the definition found in the *Diagnostic and Statistical Manual of Mental Disorders-5* (DSM-5), as confirmed with the Mini International Neuropsychiatric Interview for Children and Adolescents (MINI-KID). The MINI-KID instrument is designed to be used for children aged 6-17 years, and has been shown to have substantial to excellent concordance with the diagnosis of ADHD, among other Axis I psychiatric disorders (Sheehan et al., 2010; Leffler et al., 2015). The interview can take from 15 to 50 minutes, and can be given to parents or children, together or separately (Leffler et al., 2015).

The R-MOAS and the CGI-S scale will be administered to determine if the subject is eligible to participate in the study. Both of these scales measure severity of IA, and only those subjects with an R-MOAS score of ≥20 and a score of at least "moderately ill" on the CGI-S will be eligible for the study.

The Vitiello Aggression Scale will be used to evaluate the subtype of aggression (planned vs. impulsive); only those children who score between -2 and -5 and are considered predominantly impulsive will be included.

During the screening visit at the clinical site, subjects will have their head shape scanned (approximately 2 minutes) using a noninvasive handheld 3D scanning system from Caseforge.

3.4.2 Baseline MRI (Visit 2) and Randomization (Visit 3): Day -5 to Day 0

Baseline visits can be carried out in more than one day, within 30 days from screening. At Visit 2, subjects will receive the pre-treatment MRI scan at the Imaging Center. The subject's MRI eligibility will be re-confirmed using the MR Safety Questionnaire prior the MRI scan. To be eligible for randomization at Visit 3, subjects must have minimally completed:

- two (2) sessions of the PSAP Task fMRI and
- the MPRAGE structural scan.

Subjects unable to finish these scans will not proceed to randomization.

At Visit 3 the study site will randomize (1:1 ratio) qualified subjects to receive placebo or 36 mg/day SPN-810. Subjects will be dispensed their study medication.

3.5 Treatment Phase (4 weeks)

3.5.1 Titration Period, Day 1 to Day 14

Subjects will be instructed to titrate to reach the maintenance dose over a period of 15 days, according to the dose titration schedule shown in Figure 1 and Figure 2. Dosing will begin at SPN-810, and increase to on Day 3, 9 mg/day on Day 5, on Day 8, on Day 11, and on Day 15.

3.5.2 Maintenance Period, (14 days) Day 15 to Day 28

Following dose titration, treatment will be maintained for 2 weeks at 36 mg/day SPN-810 or placebo.

At Visit 4, before the end of the Maintenance period, blood will be drawn for quantitative PK analysis. The morning dose of study medication will be administered in the clinic. The following PK samples will be collected: pre-dose (-30 minutes), and 2, 3, 4 and 6 hours post-dose (± 15 minutes).

At Visit 4, all subjects will also have the option to participate in an OLE study (Protocol 810P304) in which all subjects will receive active treatment. At the visit, subjects will receive a blinded conversion medication card that will adjust the subject's total daily dose to 18 mg SPN-810 for initiation into the OLE (Figure 1). Those subjects who do not elect to participate in this extension study will be tapered down prior to discontinuation of the study medication and will receive a taper down card at Visit 4 (Figure 2).

At Visit 5, subjects will return to the Imaging Center for the post-treatment fMRI/PSAP Task and will use (when applicable) the same Caseforge helmet used at Visit 2.

At the completion of the MRI scans (Visit 2 and Visit 5), subjects will be administered the questionnaire to validate their understanding of the task and to describe the characteristics of their opponent. The results of the questionnaire will be provided to the study site.

3.6 Taper/Conversion Phase (7 days), Day 29 to Day 35

Subjects will complete the 1-week Taper or Conversion phase.

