3.7 End of Study (EOS)/Early Termination, Visit 6 (Day 35)

Subjects will return to the study site for a final visit, after completing the 1-week Taper or Conversion phase. Those subjects who choose to continue into the OLE study will have procedures performed for that study; eligibility criteria will be confirmed at Visit 1 of study protocol 810P304. Only the subjects who discontinue from the study during the Maintenance

period or following Day 14 in the Titration period will be offered a Taper card at the study site one week prior the EOS. All subjects who discontinue early (i.e., during the Titration period, Day 1 to Day 14) will be instructed to return to the study site for a final visit (EOS), within 1 week after discontinuation.

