4.2.1 Screening/Visit 1 (Day -30)

Prior to conducting any procedures, written Informed Consent must be obtained from the parent or LAR, and, if appropriate, Informed Assent will be obtained from the subject. Subject screening procedures will be performed within 30 days prior to titration, and may be done on more than 1 day. At Visit 1, subjects will have their head shape scanned at the clinical site using a noninvasive handheld 3D scanning system from Caseforge system. A fitted and custom designed foam helmet will be ordered to be used inside the MRI scanner (Caseforge, California). The helmet has been shown to limit head motion in an fMRI scanner (Gao et al., 2015).

The following procedures will be performed at Visit 1:

- 1. Obtain written Informed Consent and Assent.
- 2. Confirm Inclusion/Exclusion criteria.
- 3. Administer MINI-KID for ADHD diagnosis.
- 4. Administer Vitiello Aggression Scale.
- 5. Administer R-MOAS.
- 6. Administer CGI-S.
- 7. Record Medical History.
- 8. Record Demographic Information.
- 9. Perform Physical Examination.
- 10. Perform 12-lead ECG.
- 11. Collect Urine for Urine Drug Screen and Urinalysis (all subjects) and Pregnancy Test (females of childbearing potential [FOCP] only).
- 12. Record Vital Signs (Heart Rate [HR], Blood Pressure [BP], Temperature, and Respiration Rate [RR]).
- 13. Record Weight, Height, and BMI.
- 14. Collect Blood Samples for Hematology and Chemistry.
- 15. Administer C-SSRS.
- 16. Record Concomitant Medications.
- 17. Access IWRS for subject number.
- 18. Scan head shape using the Caseforge system.

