4.2.4 Maintenance/Visit 4 (Day 21)

Visit 4 will occur 21 days after the start of the Titration period. Subjects will be instructed to take their morning dose at the site. The following procedures will be performed:

- 1. Administer CGI-I and CGI-S.
- Administer R-MOAS.
- 3. Record Vital Signs (Heart Rate [HR], Blood Pressure [BP], Temperature, and Respiration Rate [RR]).
- 4. Perform Physical Examination.
- 5. Record Height, Weight, and BMI.
- 6. Perform 12-lead ECG.
- 7. Collect blood samples for PK.
- 8. Administer C-SSRS.

- 9. Administer Safety Scales (Simpson-Angus, Barnes Akathisia Rating, and AIMS).
- 10. Record Adverse Events.
- 11. Record Concomitant Medications.
- 12. Assess Drug Compliance.
- 13. Drug Return.
- 14. Dispense Study Medication (Either Conversion or Taper dose based on subject's decision to participate in OLE.

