4.2.6 Taper/Conversion/Visit 6 (Day 35)/EOS

Visit 6 will occur approximately 7 days (±2 days) following Visit 5 according to the Schedule of Events and Procedures. These procedures will be performed for all subjects who complete the Maintenance period and for those who discontinue early. Subjects who discontinue during the Maintenance period (between Day 15 and 28) will be offered a Taper card and return to the study site to complete Visit 6. Any subject who discontinues during the Titration period (Days 1-14), will be instructed to return to the study site for the final visit, within 1 week after discontinuation.

- Administer R-MOAS.
- 2. Administer CGI-I and CGI-S.
- 3. Perform Physical Examination.
- Perform 12-lead ECG.

- 5. Collect Urine for Pregnancy Test (FOCP only).
- 6. Record Vital Signs (Heart Rate [HR], Blood Pressure [BP], Temperature, and Respiration Rate [RR]).
- 7. Record Height, Weight, and BMI.
- 8. Collect Blood for Hematology and Chemistry.
- 9. Collect Urine for Urinalysis.
- 10. Administer C-SSRS.
- 11. Administer Safety Scales (Simpson-Angus, Barnes Akathisia Rating, AIMS).
- 12. Record Adverse Events.
- 13. Record Concomitant Medications.
- 14. Collect Study Medication and Assess Treatment Compliance.
- 15. Obtain written Informed Consent and Assent for OLE study.
- 16. Complete/Discontinue Subject.

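### For subjects who complete Maintenance, the only scheduled post-baseline laboratory sample follows a week of taper or conversion to SPN-810, yet the SAP tabulates it by treatment group alone

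*Protocol*

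**What the plan says.** **Laboratory sampling.** The Visit 1 list (Protocol 4.2.1) has "Collect Blood Samples for Hematology and Chemistry", with urinalysis. The Visit 4 list (4.2.4) has "Collect blood samples for PK" and no safety laboratory draw. Visit 5 (4.2.5) has none. The Visit 6 list (4.2.6) has "Collect Blood for Hematology and Chemistry", with urinalysis. Table 1 of the Protocol agrees.

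**What happens before Visit 6.** Protocol 3.7 states: "Subjects will return to the study site for a final visit, after completing the 1-week Taper or Conversion phase". Section 4.2.6 gives the timing: "Visit 6 will occur approximately 7 days (±2 days) following Visit 5". Section 3.5.2 says that "all subjects will also have the option to participate in an OLE study (Protocol 810P304) in which all subjects will receive active treatment", and of those who accept, "subjects will receive a blinded conversion medication card that will adjust the subject's total daily dose to 18 mg SPN-810". Those who decline are tapered. Section 5.1.1 puts one Taper card and one Conversion card in every kit, and section 5.1.7 keeps the blind through this phase.

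**Early stoppers.** They also attend Visit 6. Section 4.2.6 says: "Subjects who discontinue during the Maintenance period (between Day 15 and 28) will be offered a Taper card". Subjects who stop during Titration return within a week, and no card is mentioned for them.

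**SAP.** Section 7.6.2 summarises laboratory values by visit and arm and builds shift tables within arm. Section 7.6.3 gives vital-sign change only to the final visit. Section 7.6.1 runs TEAEs to study end, with extra tables for Titration, Maintenance and the two combined. Section 7.6.6 gives C-SSRS by arm and names no visit. Section 7.3 stops exposure and compliance summaries at the end of Maintenance. No section separates the Taper/Conversion phase or says what each subject took in it.

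**The concern.** A reader of a Visit 6 table with columns for SPN-810 36 mg and placebo will take it as a comparison of those two treatments. For Maintenance completers it is not. On the visible text, a placebo subject who chose the extension is counted under placebo after receiving SPN-810. An active-arm subject is counted under 36 mg after a taper or a change to 18 mg.

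The laboratory tables suffer most because nothing else stands beside them. Protocol 1.6 promises an evaluation of metabolic parameters and prolactin, and Visit 6 is their only scheduled post-baseline measurement. Similar columns could be read as no drug effect when the treatments taken had converged. SAP 6.1 makes every analysis descriptive after early termination, so the risk is a misread safety table rather than a biased test.

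**Working it through.** There is no stated figure to reproduce; this is a comparison of the visit schedule with the planned tables.

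**Step 1. Laboratory samples in a Maintenance completer** (Protocol 4.2.1 to 4.2.6, Table 1)

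| Visit | Nominal day | Haematology, chemistry, urinalysis | Treatment period |
|---|---|---|---|
| 1 | -30 | Yes | Before treatment |
| 4 | 21 | No (PK blood only) | Maintenance |
| 5 | 28 | No | Maintenance |
| 6 | 35 | Yes | After Taper/Conversion |

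Scheduled post-baseline samples: 1. Of these, on the Maintenance dose: 0. Visit 6 falls 7 ± 2 days after Visit 5, that is 5 to 9 days. The qualifier *scheduled* matters, because repeat or unscheduled tests are possible.

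**Step 2. Who is present at Visit 6.** Each arm can contain three groups: Conversion, Taper, and neither (for example Titration dropouts). SAP 7.1 puts everyone who was randomised and dosed in the Safety Population, so all three sit in one column per arm.

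**Step 3. Which summaries are affected**

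| Summary | By-arm result on randomised treatment | Mixes in the Taper/Conversion week |
|---|---|---|
| Laboratory values and shifts (SAP 7.6.2) | None scheduled | Yes, at Visit 6 |
| Vital signs (7.6.3) | Visit 4 actual values, but change is specified only to final visit | Yes, in the change |
| ECG (7.6.4), EPS scales (7.6.7), CGI and R-MOAS (7.7.2) | Visit 4 rows | Only in the Visit 6 rows |
| TEAEs (7.6.1) | Titration, Maintenance and combined tables | Only in the table to study end |
| C-SSRS (7.6.6) | Not identifiable, as no visit is named | Yes, if visits are pooled |

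**Step 4. Size of the windows.** For a completer, the TEAE window to study end covers Days 1 to 35, of which Days 29 to 35 follow Maintenance: 7/35 = 20% of days. This is a share of time, not of events. The C-SSRS at Visit 6 asks about the period since Visit 4 (Protocol 6.3.9.4). Nominally that is Days 22 to 35: 7 Maintenance days and 7 Taper/Conversion days.

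**Step 5. Illustration of how many placebo subjects could convert.** Expected converters = placebo completers × uptake. The planned arm is 15 (Protocol 4.1); 10 and 5 are assumed, because numbers after early termination are not given. Uptake of 25% is assumed. The second rate is 78/121 = 64.5%, from a different sponsor study (Protocol 1.5), with all randomised subjects as its denominator rather than completers.

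| Placebo completers | 25% uptake | 64.5% uptake |
|---|---|---|
| 15 | 3.75 | 9.67 |
| 10 | 2.50 | 6.45 |
| 5 | 1.25 | 3.22 |

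These count subjects. They do not measure distortion of any laboratory value.

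**The case against.** The strongest reply is that most of the safety plan already copes. Visit 6 is a separate row in the by-visit summaries, and Table 1 heads it as Taper/Conversion. ECG, EPS and behavioural scales have Visit 4 rows. The Titration and Maintenance TEAE tables leave out the last week, and listings are planned. The mention in SAP 7.6 of EPS worsening to the end-of-study visit is overview wording; SAP 7.6.7 gives Visit 4 separately. Reporting by randomised arm is also an accepted convention. All of this stands, and it confines the point to the laboratory tables, the vital-sign change, the TEAE table to study end and the C-SSRS summary.

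Second, a reader might infer that placebo converters took 18 mg/day throughout the week. The documents do not support that much. The text gives 18 mg SPN-810 for entry to the extension and makes no exception for placebo, but the day-by-day schedule is in Figure 1, which is not shown. Some exposure is a fair inference; its amount and duration are unknown.

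Third, it is tempting to replace final visit by Visit 4 altogether. That would remove subjects who stop before Visit 4 from the by-arm comparison, since Visit 6 is their only scheduled post-baseline assessment.

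Fourth, two arms by three groups gives six cells. Even at the planned 30 subjects that averages 30/6 = 5 per cell, and the study ended early. This is a fair practical limit, and listings may have to do the work.

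**Conclusion.** The point holds in limited form and is worth fixing. For Maintenance completers, 0 of 1 scheduled post-baseline laboratory samples is on the Maintenance dose, and SAP 7.6.2 labels that sample by treatment group with nothing to show what was taken in the preceding week. The vital-sign change to final visit and the TEAE table to study end share the problem to a lesser degree, and the C-SSRS summary needs its visits separated.

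The conclusion rests on the visible text: conversion is open to all subjects, and no placebo exception appears. It does not rest on the converter counts, which are illustrative. It does not extend to imaging, to the Visit 4 summaries (including the CGI and R-MOAS endpoints, which the Protocol Synopsis sets at Visit 4), or to the Titration, Maintenance and combined TEAE tables. A reader might infer that the whole safety comparison is unsound or that a test is biased. Neither follows: on-treatment comparisons exist for everything in the second list, and nothing is tested.

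**What to change.** Change the SAP only.

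- **Laboratory (7.6.2).** Present Visit 6 values and shift tables by randomised arm and by treatment taken after Maintenance or discontinuation: Conversion, Taper or neither. Where cells are too small, flag the group in the listings instead. State that, for Maintenance completers, these values are not an on-treatment comparison of 36 mg with placebo.
- **Vital signs (7.6.3).** Add change from baseline to Visit 4 as the by-arm summary on randomised treatment. Keep the final-visit summary beside it so that subjects who stop before Visit 4 stay visible. Label Visit 6 as Taper/Conversion or early termination.
- **TEAEs (7.6.1).** Use the planned combined Titration and Maintenance table as the by-arm comparison. Show Taper/Conversion-phase onsets separately, with the same cut-off that the Maintenance table already needs.
- **C-SSRS (7.6.6).** Report Visit 4 and Visit 6 separately, noting that the Visit 6 recall period spans late Maintenance and Taper/Conversion.

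**Cost.** One derived variable for treatment taken, and revised table shells. The card dispensed at Visit 4 is not enough to derive it, because Maintenance dropouts may be given a Taper card later. The discontinuation record and the medication returned and compliance assessed at Visit 6 are also needed. The eCRF is not among the documents, so whether the first Taper/Conversion dose date was recorded cannot be checked; using the existing Maintenance cut-off avoids depending on it.

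**Downside.** Visit 6 subgroups will be very small. With 10 placebo completers and 64.5% uptake, about 6.45 would convert and 10 − 6.45 = 3.55 would taper, so listings may carry most of the information. No SAP edit can supply the missing on-treatment laboratory sample.
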